PROTOCOL TITLE: Topiramate for infants receiving whole body cooling in neonatal encephalopathy

NCT01765218

Document Submission Date to IRB 6/6/2018

Last IRB Review of Study 3/28/2023

PROTOCOL TITLE: Topiramate for infants receiving whole body cooling in neonatal encephalopathy

1) Protocol Title

Title: Topiramate for infants receiving whole body cooling in neonatal encephalopathy

Protocol Version Date: May 25th, 2018

2) Objectives

- a) Specific Aims: To determine the effect of adjuvant topiramate treatment on the outcome of newborns with perinatal depression (including neonatal encephalopathy) who are already receiving the therapeutic whole body cooling.
- b) Hypotheses: We hypothesize that adjuvant therapy with topiramate will reduce short term disease severity in infants with neonatal encephalopathy/perinatal depression who are receiving whole body cooling. Specifically, we hypothesize that adjuvant topiramate will reduce the incidence of seizures (the primary outcome) in these infants. Secondary objectives include assessing the effect of that adjuvant topiramate in infants with neonatal encephalopathy/perinatal depression on biochemical markers of neuronal damage (serum UCHL1/ urine S100 β levels), a composite score of aEEG/cEEG abnormality, and on developmental outcomes at 9m, 18m and 27m.
- c) Scientific Problem: Neonatal encephalopathy is a devastating and unexpected disease in newborns that affects 1.5 to 2.6 per 1000 live births (Kurinczuk 2010). Neonatal encephalopathy has a mortality rate of up to 30% and survivors are at significant risk for adverse outcomes, including seizures, cerebral palsy, and neurodevelopmental delay. Until recently, only supportive care could be offered to these infants, and no therapy was available to modify the natural history of the disease. However, therapeutic hypothermia, or whole body cooling, has been shown to be beneficial for these infants. Hypothermia reduces mortality and decreases the risk of moderate to severe handicap in survivors. (Shankaran 2005).

Although whole body cooling is effective at reducing the mortality and morbidity of neonatal encephalopathy/perinatal depression, the long-term outcome for such babies remains poor. For example in a recent NICHD funded study, whole body cooling reduced the rate of death but had no significant effect on long-term neurodevelopmental outcome of the survivors or moderate or severe disability from 62% to 44% (Shankaran 2012).

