Newborn infants diagnosed with neonatal encephalopathy undergoing cooling therapy for neonatal encephalopathy irrespective of gender or race are eligible for this study. We aim to recruit patients both in English and Spanish.

All four of the following criteria must be met to qualify for the cooling protocol

1. Age: less than 1 day old
2. Gestational age > 35wks
3. Evidence of birth depression, either
 - a. 10 minute Apgar score less than 5
 - b. Need for cardiopulmonary resuscitation at 10 minutes of age
 - c. Blood pH < 7.0 within the first 1-hour of life
 - d. Base excess lower than -12 (i.e. base deficit more than 12) within the first hour of life
4. Evidence of encephalopathy based on clinical (neurological examination) or on aEEG/cEEG assessment.

Exclusion Criteria:

1. Major congenital or genetic abnormalities
2. Infants more than one day old
3. Known allergy/sensitivity or any hypersensitivity to components of study drug
4. Maternal illicit drug or alcohol use during pregnancy
5. If the baby had a proven (i.e. electrically confirmed seizure) prior to enrollment

5) Study Timelines

We expect to complete this study within 2 years. We have 13 patients already enrolled and our goal is 42 total (study arm n=21 and control arm n=21). We have chosen a sample size of 42 as this sample size will have an 80% chance of detecting a reduction of seizure rate by 2/3 with a p-value of 0.05.

At our institution alone we have ample experience in whole body cooling having cooled 31 patients in 2015, 28 patients in 2016, and most recently 26 patients in 2017. Patients will be asked to come for a one hour follow up outpatient clinic (MIND Institute) visit at the at 9, 18, and 27 months of age (all infants who receive cooling are asked to complete this follow-up, including those not in this study).

6) Study Endpoints

Our primary study endpoint remains to conclude if our current modality of whole-body cooling coupled with topiramate results in seizures or no seizures.

As well to determine the effect of adjuvant topiramate treatment on the outcome of newborns with perinatal depression (including neonatal encephalopathy) who are already receiving the therapeutic whole body cooling.

7) Informed Consent

One or both parents of the eligible infants are approached either

- (1) In person in the NICU at UCDMC by one of the investigators
- (2) By our Transport Nursing staff or Neonatal Fellow (if they are still at the outside referral center)

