In either case, the details of the study its risks and potential benefits will be explained by an investigator, and the parents are allowed to make an informed choice as to whether or not they decide to participate. If patient is transported the parents will be supplied with a copy of the consent form by the transport team and then contacted directly by an Investigator or when they arrive to our NICU.

- Provide the consent form in person, give prospective subject sufficient time to review the consent form and discuss with friends/family.
- Consent forms will also be given to the parents by the neonatology transport team and contacted directly by an Investigator.

8) Procedures Involved

This is a randomized double blind placebo controlled trial of newborns with neonatal encephalopathy undergoing our standard clinical protocol of whole body cooling. We will approach the parents of eligible infants, describe the study to them, and ask if they want their baby to participate in the study. Infants will be randomized by UCDMC pharmacy to receive cooling with placebo (control arm, n=21) or cooling with topiramate (study arm, n=21). At UC Davis, whole body cooling is a standard treatment for all infants with neonatal encephalopathy.

Active cooling will begin as soon as an infant is admitted to our NICU, using whole body cooling with a goal core temperature of 33.5 degrees Celsius and will be continued for 72 hours. Subject temperature will be monitored continuously using a rectal temperature probe and skin integrity is monitored closely with frequent turning of the

PROTOCOL TITLE: Topiramate for infants receiving whole body cooling in neonatal encephalopathy

infant. After 72h of cooling, babies are slowly rewarming back to normal body temperature over a period of 12h.

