The Pediatric Neurology service is by protocol consulted on all cooling patients. They will evaluate the infant and determine a neonatal encephalopathy score daily under the supervision of our Pediatric Neurologists. The presence of clinical seizures will be noted based on review of the bedside aEEG or cEEG. The aEEG/cEEG data will be reviewed in 3 hour increments and document the time when the voltages on the aEEG/cEEG first return to normal. The aEEG/cEEG is used throughout the cooling phase and is generally discontinued after rewarming is completed but may be continued longer for abnormal tracings such as seizures at the discretion of the Neonatology Attending. In addition, the Attending Pediatric Neurologist will assess quality of movements, posture, reflexes, and muscular tone, each infant's neurologic status will be categorized as normal (completely normal neurologic status), unspecific signs (eg, asymmetric muscle tone or reflexes) or abnormal with lack of reflexes and bilateral muscular hypotonia or hypertonia.

Additional tests in infants enrolled in this research study include: serum UCHL1 and urine levels of S100 β , both will be measured at enrollment, at the start of rewarming, and at one-week of life. Topiramate trough drug levels will be collected 24 hours after the first, third, and fifth doses. The drug levels will be run by the UCDMC laboratory. These

PROTOCOL TITLE: Topiramate for infants receiving whole body cooling in neonatal encephalopathy

are the only additional laboratory assessment that study infants will receive as a result of taking part in the study.

All infants on the cooling protocol, irrespective of the research study, will have an MRI with spectroscopy on day 5-7 of life. For this study, these images will be read by a single radiologist, our collaborator [name] of Neuroradiology. The reporting of MRI and MRS results will be standardized in conjunction with [name] to create a more consistent scoring method.

Following discharge, each infant will receive long-term developmental follow-up through the MIND clinic our High Risk Infant follow-up clinic. Infants will be seen at approximately 9, 18, and 27 months. The infants will have standardized Bayley Scale of Infant Development (BSID) III neurodevelopmental screening at these clinic follow-ups supervised by [name].

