The BSID-III contains 3 domains: cognitive, language (receptive and expressive communication), and motor (fine and gross motor). The cognitive scale includes items that assess sensory perceptual development, exploration and manipulation, object relatedness, concept formation, memory, and other aspects of cognitive processing. To allow comparison of results from the 3 domains, a composite score is calculated for each domain (mean, 100). A composite score below -2 SD (<70) is considered a severe delay for all domains. A Pediatrician will assess the quality of movements, posture, reflexes, and muscular tone at each clinic visit. Each infant's neurologic status will be categorized as normal gait and walking, unspecific neurological signs (eg, asymmetric muscle tone or reflexes, muscular hypotonia), or abnormal with upper and/or lower extremities muscular hypertonia (signs of cerebral palsy (CP) present).

9) Data and/or Specimen Management and Confidentiality

Power Calculation

Our primary hypothesis is that topiramate will reduce the frequency of early seizures (i.e. before hospital discharge). From our current data, 64% of infants have seizures prior to hospital discharge; a sample size of 42 will have an 80% chance of detecting a reduction of seizure rate by 2/3 with a p-value of 0.05.

Statistical Methods

Our primary outcome is that seizures before hospital discharge will be significantly reduced in the topiramate group compared to the controls. This will be assessed by nominal logistic regression with the presence or absence of seizures as the nominal dependent variable, and treatment group (topiramate or control) as an independent variable. Other independent variables will include those that are unbalanced between the treatment groups at randomization, and factors that could affect the risk of seizures (these would include neonatal encephalopathy score at study entry, time to initiation of cooling (< or \geq 3h), gender etc).

The effect of treatment assignment on neonatal encephalopathy score (measured daily) will be assessed by repeated measures ANOVA with neonatal encephalopathy score as the dependent variable, time and treatment assignment as the independent variable, and addition independent variables included as appropriate (see above). Time to normalization of aEEG/cEEG in the two different groups will be assessed by Kaplan-

PROTOCOL TITLE: Topiramate for infants receiving whole body cooling in neonatal encephalopathy

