Meier analysis. The effect of treatment on S100 β levels in the urine or UHCL1 in the blood and on other markers of tissue injury will be compared using ANOVA (for outcomes measured once) and by repeated measures ANOVA for those measured on more than one occasion, at predetermined times.

Effect of treatment assignment of development assessments will be assessed individually at the 9m, 18m and 27m examinations.

All tests will be considered significant at $p<0.05$. Where necessary, Tukey-Kramer's test will be used to account for multiple comparisons

Data Specimen/Management

Data specimens will be stored in the NICU and numerically coded, only those who are involved with this study will have access to the specimens. The specimens will only be stored for the duration of the study and thereafter discarded.

10) Data and/or Specimen Banking

There is no plan for specimen or tissue banking in the future.

11) Provisions to Monitor the Data to Ensure the Safety of Subjects

To monitor the safety of each newborn we will track the following variables closely during the intervention: blood gases, blood pressure (hypotensive episodes and required interventions), evidence of seizure activity, and serum topiramate levels. This study is only applicable to newborns with neonatal encephalopathy admitted to the NICU at UC Davis for cooling therapy. Neonatal encephalopathy is a life threatening disease with 30% chance of death and 64% chance of seizures during the neonatal period. These patients receive 24 hours daily continuous extremely close physiological and biochemical monitoring based on their underlying disease state.

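### Time to aEEG/cEEG normalisation is assigned to Kaplan-Meier with no rule for infants who die before normalising; the default, censoring at death, would overstate recovery on this secondary endpoint

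*Combined protocol and SAP*

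**What the plan says.** The analysis is named in one sentence of section 9 (Statistical Methods): "Time to normalization of aEEG/cEEG in the two different groups will be assessed by Kaplan"-Meier analysis. No test, estimand or censoring rule follows.

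Section 8 (Procedures Involved) supplies the event. The tracings are reviewed in 3-hour blocks, and staff are to "document the time when the voltages on the aEEG/cEEG first return to normal". Death is not part of that event. Recording normally stops once rewarming is complete, but may go on longer for an abnormal tracing at the attending's discretion.

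The usual window follows from the cooling schedule in the same section: a "goal core temperature of 33.5 degrees Celsius and will be continued for 72 hours", after which "babies are slowly rewarming back to normal body temperature over a period of 12h".

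Mortality appears twice. Section 2 says "Neonatal encephalopathy has a mortality rate of up to 30" per cent. Section 11 says "Neonatal encephalopathy is a life threatening disease with 30% chance of death and 64% chance of seizures during the neonatal period".

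Section 4 accepts "Evidence of encephalopathy based on clinical (neurological examination) or on aEEG/cEEG assessment", so an infant can qualify on clinical signs alone.

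**The concern.** Kaplan-Meier knows two states: event, or censored. Censoring assumes that an infant who leaves the risk set would have gone on to normalise at the same rate as those still under observation. An infant who dies with an abnormal tracing cannot normalise, so death is a competing event. If such infants are censored at death, the curve describes recovery in a hypothetical setting without death and lies above the proportion who actually recovered.

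The comparison between arms is also exposed. An arm with more early un-normalised deaths has its curve raised more. It can then look equal or better while fewer of its infants recovered. With 21 infants per arm, a handful of deaths is enough.

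**Working it through.** The plan gives no figure for this endpoint, so there is none to reproduce. Its sample size of 42 rests on seizures.

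**Inputs from the documents**
- Recording window: 72 h cooling + 12 h rewarming = 84 h (section 8).
- Arms: 21 and 21 (sections 5 and 8).
- Mortality: 30%, for the neonatal period (section 11); up to 30% (section 2).

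**Assumed, because the documents do not give them**
- Share dying un-normalised within 84 h: 5%, 10%, 20%.
- Kaplan-Meier reading at 84 h: 70% or 80% normalised.
- Constant hazards of normalisation and of death, deaths censored at death.

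**Step 1: what a given reading means.** Let A and B be the cumulative hazards over 84 h of normalisation and of death before normalisation.
- Kaplan-Meier reading = 1 − exp(−A), so A = −ln(1 − reading).
- Share dying first = B/(A+B) × [1 − exp(−(A+B))]; solve for B.
- Share truly normalised = A/(A+B) × [1 − exp(−(A+B))].

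Example, reading 70% with 10% dying first: A = −ln(0.30) = 1.204 and B = 0.185. Then A+B = 1.389 and 1 − exp(−1.389) = 0.751. Deaths: 0.185/1.389 × 0.751 = 0.100, as required. Normalised: 1.204/1.389 × 0.751 = 0.651.

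| Kaplan-Meier reading | 0% die first | 5% | 10% | 20% |
|---|---|---|---|---|
| 70% | 70% | 67.6% | 65.1% | 59.9% |
| 80% | 80% | 77.0% | 73.9% | 67.6% |

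At a reading of 70% the overstatement is 2.4, 4.9 and 10.1 points. In an arm of 21 that is 0.024 × 21 = 0.5, 0.049 × 21 = 1.0 and 0.101 × 21 = 2.1 infants.

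**Step 2: effect on the comparison.** Suppose all deaths in an arm occur at 24 h, before any normalisation, and nobody else is censored before 84 h. If D infants die and N normalise, the true proportion is N/21 and the Kaplan-Meier reading is N/(21 − D).

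| Arm (illustration) | D | N | True proportion | Kaplan-Meier reading |
|---|---|---|---|---|
| Control | 1 | 14 | 14/21 = 66.7% | 14/20 = 70.0% |
| Topiramate | 5 | 11 | 11/21 = 52.4% | 11/16 = 68.8% |
| Topiramate, one more death | 6 | 11 | 11/21 = 52.4% | 11/15 = 73.3% |

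With 5 deaths against 1, a true deficit of 66.7 − 52.4 = 14.3 points appears as 70.0 − 68.8 = 1.2 points. With 6 against 1 the order reverses, 73.3% against 70.0%.

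**Step 3: when the problem vanishes.** Deaths after recording ends, or after normalisation, do not bias the curve. Nor do deaths kept in the risk set as not normalised to a common horizon: each reading in Step 2 then becomes N/21.

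**The case against.** The strongest reply is that the documents never say deaths are censored. Keeping infants who die in the risk set to a fixed horizon is also a Kaplan-Meier analysis, so a reader who infers that the plan prescribes censoring at death goes beyond the text. That stands: what can be shown is a missing rule whose usual default is biased.

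A reader might also apply the 30% mortality directly. If all of it fell un-normalised inside 84 h, a 70% reading would mean 54.5%. The documents do not support this. The figure covers the whole neonatal period, section 2 words it as an upper bound, and the same section says cooling lowers mortality; every trial infant is cooled. Even the 20% column is unsupported by any figure in the plan. At 5% the overstatement is about half an infant per arm, well inside a binomial standard error of √(0.7 × 0.3/21) = 10 points. Masking also needs clearly unequal early deaths, as in the illustration.

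A third inference, that harm would be hidden from the trial, also fails. Under section 11 the safety committee receives survival to discharge by coded arm every 6 months and may unblind itself on an adverse trend at P<0.1. However, survival is not an outcome in Statistical Methods, so no planned analysis would sit beside this curve to correct it.

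Finally, censoring deaths gives a legitimate comparison of normalisation rates among infants still alive and abnormal. That is true, but it does not make the curve a proportion recovered, and the plan does not say which is wanted.

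**Conclusion.** The point holds as a gap in a secondary analysis that should be closed. The plan names a method with no place for death, in a population it describes as having high mortality, and states no rule. If un-normalised deaths in the window are censored, the recovery percentage is biased upwards. At a reading of 70% the bias is about 2, 5 or 10 points for 5%, 10% or 20% such deaths, and zero if there are none. Those shares and the constant hazards are assumptions; the documents do not fix the true size.

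Masking or reversal between arms is possible but conditional on unequal early deaths, and is confined to this endpoint. The primary logistic regression and the sample size are untouched. Time to normalisation is not among the secondary objectives in section 2, which lists a composite EEG abnormality score instead; this limits the weight of the point.

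Some infants may enter with a normal tracing, for whom a first return to normal is undefined. Their number is unknown, and the conclusion does not depend on them.

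**What to change.** Add a short paragraph to Statistical Methods before unblinding, adopting one of two approaches:

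- **Competing event.** Estimate the cumulative incidence of normalisation with death as a competing event (Aalen-Johansen) and compare arms with Gray's test.
- **Fixed horizon.** Keep infants who die un-normalised in the risk set as not normalised up to a common horizon, such as the planned end of rewarming (72 h + 12 h = 84 h). Censor infants still abnormal at that horizon there, even if their recording continues. A common horizon is needed because recording may be extended for abnormal tracings, so follow-up would otherwise depend on the outcome.

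Under either approach, define time zero, report the number of un-normalised deaths per arm beside the curve, and state how infants with a normal tracing at time zero are handled. If they are excluded, that should be decided on the time-zero tracing, read blind to assignment.

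The cost is a few sentences. Beyond the time of death the data are those already planned, and the software is standard. The downside is that recovery percentages will look slightly lower than a plain Kaplan-Meier curve would show.

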Infants assigned to the topiramate group will receive 5mg/kg of topiramate daily enterally for a total of 5 doses. This is the minimum therapeutic dose of topiramate for infants. The first dose will be administered on the day of enrollment and will continue through and after rewarming. The duration of drug administration was chosen to encompass the cooling period as well as a brief period after rewarming is complete as this is a period where some infants develop seizures and display more signs of neurological damage. The control group will receive a placebo instead of topiramate. Pharmacy will prepare and send to NICU the placebo or study drug solutions in a way to be similar in appearance and volume. Initiation of cooling will not be delayed, but families will be approached for consent as soon as possible after cooling has started.

The cooling protocol includes a range of laboratory evaluations which will be carried out irrespective of whether the patient is enrolled in the study. These include: complete blood count, PTT/INR, DIC panel, complete metabolic panel, ammonia, lactate, troponin-I, CK panel, blood gas, and urinalysis at the initiation of cooling and then every 24h until rewarming is complete (unless the Attending Neonatologist decides that more frequent or less reassessments are needed clinically). Blood gases, blood glucose and ionized calcium levels are measured at the initiation of cooling and then every 6h until rewarming is complete. Once labs have normalized per the discretion of the covering Attending some of these labs may be discontinued. These lab values will provide important data of the severity of each infant's hypoxic-ischemic insult and for patient safety monitoring including information on liver function, kidney function, ammonia toxicity, metabolic status, and acidosis. Enrollment in the study will not change the frequency of these assessments.

A single channel EEG recording (an amplitude EEG, aEEG) or continuous video EEG is recorded continuously on all patients until rewarming is complete. This method measures the degree of encephalopathy and detects seizures.

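### Time to aEEG/cEEG normalisation is compared unadjusted and with no test named; a pre-specified Cox model with the entry encephalopathy score would be valid and could be more powerful if the score is prognostic

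*Combined protocol and SAP*

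**What the plan says.** Section 9, Statistical Methods, gives the EEG recovery endpoint one sentence: "Time to normalization of aEEG/cEEG in the two different groups will be assessed by Kaplan"-Meier analysis. Nothing else in the documents adds a test, a covariate, a stratification factor or a regression model for it.

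The neighbouring analyses read differently. For the primary logistic model of seizures, the section lists factors that could affect risk: "these would include neonatal encephalopathy score at study entry, time to initiation of cooling" and others. The repeated measures ANOVA of the daily encephalopathy score takes "addition independent variables included as appropriate (see above"). The Kaplan-Meier sentence comes next and has no such cross-reference.

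Section 8 shows that the data exist. Pediatric Neurology is to "determine a neonatal encephalopathy score daily under the supervision of our Pediatric Neurologists". The EEG is "reviewed in 3 hour increments and document the time when the voltages on the aEEG/cEEG first return to normal", and recording "is generally discontinued after rewarming is completed but may be continued longer for abnormal tracings". Of the EEG itself the section says: "This method measures the degree of encephalopathy and detects seizures".

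Time to normalisation appears only in the procedures and the methods. The secondary objectives in Section 2 list biomarkers, a composite score of EEG abnormality and developmental outcome, but not this endpoint.

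**The concern.** The plan treats entry severity as worth adjusting for in its primary analysis, then gives a related neurological endpoint a method that cannot take a continuous covariate. The endpoint is the recovery time of a measure of encephalopathy, and the omitted covariate is the clinical grade of the same condition at baseline. If the two are related, an unadjusted comparison leaves explainable variation in the noise, and a real effect on EEG recovery is more likely to be missed.

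The trial is small: "our goal is 42 total (study arm n=21 and control arm n=21"). Section 8 has the pharmacy randomise and mentions no stratification by severity, so the design does not recover the lost information either. Adjustment is also most credible when fixed in advance; if added after unblinding it could be challenged as data-driven.

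**Working it through.** **The plan's own figure.** The only power statement is for seizures: 64% reduced by two thirds to 21.3%, 80% power, p 0.05, 42 infants. With a pooled two-sided test and no continuity correction, n per arm = [1.96·√(2 × 0.4267 × 0.5733) + 0.8416·√(0.64 × 0.36 + 0.2133 × 0.7867)]² / 0.4267² = 19.9, so 20 per arm or 40 in total. Power at 21 per arm is 82.3%. The 42 is reproduced to within two infants, but it says nothing about the EEG endpoint, for which no power, effect or event count is stated.

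**Scale of the EEG endpoint.** Schoenfeld power is Φ(½·√d·ln HR − 1.96). If all 42 infants normalise under observation:
- HR 2.0: ½ × 6.481 × 0.693 − 1.96 = 0.29, power 61%.
- HR 2.5: ½ × 6.481 × 0.916 − 1.96 = 1.01, power 84%.

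At HR 2.0, 80% power needs 4 × (1.96 + 0.8416)² / 0.693² ≈ 66 events. There is little power to spare.

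**Simulation of adjusted against unadjusted tests.**
- From the documents: 21 per arm; event times on a 3-hour grid; censoring at 84 h (72 h cooling plus 12 h rewarming, Section 8); significance level 0.05.
- Assumed, because the documents are silent: two-sided testing; exponential times; control median 36 h at the average score; a normally distributed score measured without error; the treatment HR; and the factor by which each SD of worse score reduces the hazard of normalising.
- Tests: unadjusted log-rank, and a Cox likelihood-ratio test for treatment with the score in the model. There were 2,500 runs per cell, so the Monte Carlo SE is at most √(0.25/2500) = 1 point.

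| Treatment HR | Score HR per SD (log-hazard) | Log-rank power | Adjusted Cox power | Difference, points |
|---|---|---|---|---|
| 2.5 | 1.0 (0) | 79.1% | 78.2% | −0.9 |
| 2.5 | 1.5 (0.41) | 69.9% | 75.7% | +5.8 |
| 2.5 | 2.0 (0.69) | 58.8% | 76.6% | +17.8 |
| 2.5 | 3.0 (1.10) | 41.8% | 72.1% | +30.3 |
| 2.0 | 1.0 (0) | 54.2% | 52.8% | −1.4 |
| 2.0 | 1.5 (0.41) | 47.3% | 53.4% | +6.1 |
| 2.0 | 2.0 (0.69) | 37.1% | 51.4% | +14.3 |
| 2.0 | 3.0 (1.10) | 25.5% | 47.4% | +21.9 |

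With no treatment effect, both tests rejected in 4.5% to 6.6% of runs.

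**Less favourable assumptions** (1,500 runs per cell, SE about 1.3 points or less). At a treatment HR of 1.5 the gain is about 2 to 4 points for log-hazards of 0.3 to 0.7, even with an error-free score. If the score's reliability is 0.6 (an assumption), the gain is roughly 5 to 10 points at HR 2.0 to 2.5 with log-hazards of 0.5 to 0.7. The error-free gain in that same region is about 11 to 18 points.

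**The case against.** The case for leaving the plan alone has several sound parts.

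- **Validity.** Randomisation makes the unadjusted comparison valid, and the simulated type I error is near 5% for both tests. A chance imbalance in severity is not rare: the SE of the difference in mean score is √(2/21) = 0.31 SD, so a difference above 0.3 SD arises in about one trial in three. The test's error rate already allows for that. A reader might infer that the unadjusted curves are biased; they are not. The smaller unadjusted hazard ratio is a different estimand, and Kaplan-Meier does not estimate a hazard ratio.
- **Dependence on assumptions.** The documents do not name the score or give its range. Measurement error is plausible, since cooled infants are routinely sedated with morphine (Section 13) and consent is sought after cooling has started (Section 8).
- **Status.** No power is claimed for this endpoint, and it is outside the objectives in Section 2. It is also not the only analysis without covariates: the biomarker ANOVAs name none. Because no test is named, the text does not exclude a stratified log-rank test.
- **Other gaps.** The plan does not say how to treat death before normalisation (Section 11 cites a 30% risk), a tracing already normal at entry (Section 4 allows encephalopathy to be shown clinically), or recording prolonged for abnormal tracings. A Cox model settles none of these, and the simulation includes none of them.

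All of this limits the size and weight of the point. None of it is a reason to prefer the unadjusted test: the simulated cost of adjusting for a score with no prognostic value is about 1 point.

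**Conclusion.** The point holds as one of efficiency. The plan has a baseline value that plausibly predicts this endpoint, uses it in the primary model, and does not use it here. The likely gain from adjustment at 42 infants is:

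- about 0 points if the score is not prognostic;
- 2 to 4 points for a weak score or a treatment HR of 1.5;
- about 5 to 18 points for a moderately prognostic score at HR 2.0 to 2.5, depending on measurement error;
- over 20 points only for a strong score measured without error.

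These figures rest on the assumed median, hazard ratios and score distribution. The documents supply none of them, so no single figure is defensible. A reader might infer that power is certainly being thrown away; the documents do not support that, because they never say how well the score predicts EEG recovery. The point does not affect the primary analysis or the sample size.

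**What to change.** In Section 9, keep the Kaplan-Meier curves as the display and add wording such as: the arms will be compared by a Cox model for time to normalisation with treatment and the encephalopathy score at study entry (continuous, 1 df), using the likelihood-ratio test for treatment and reporting the adjusted hazard ratio with its 95% CI; ties from the 3-hour grid will be handled by Efron's method; proportional hazards will be checked; the unadjusted log-rank test will be reported as a sensitivity analysis.

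Settle this before unblinding. In the same edit, state whether the endpoint is secondary or exploratory, and how the analysis treats deaths, tracings normal at entry and the end of recording.

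The cost of the main change is one sentence and one extra model on data already collected. It also supplies the between-arm test that is now missing. The downside is small: the hazard ratio is conditional on the score, so it differs in meaning from an unadjusted one, and it assumes proportional hazards, which 42 infants can check only roughly.
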